Title:	Povidone-Iodine Oral Rinse Study: A 2-phase, Randomized Trial to Test the Effects of Povidone-iodine 0.5% as Mouthwash/Gargle on SARS-CoV-2 (COVID 19) Load as an Adjuvant Infection Control Measure in Dental Practice
Brief Title:	Povidone-Iodine Oral Rinse Study
NCT Number:	05239598
IRB Number:	849386
Version Date:	5/13/2022

Protocol

Abstract

This study is a two-arm, randomized, 2-phase study. Phase I will be double blinded clinical trial of the safety and efficacy of an antiseptic mouth rinse solution on reducing SARS-CoV2 load in COVID 19+ adult individuals. Phase II is designed as an open label trial, and all subjects will receive the active mouthwash.

Objectives

Overall objectives

Primary Objective: is to test the efficacy of Povidone-iodine 0.5% when used as a mouth rinse on reducing SARS-CoV-2 load in the oral cavity of COVID-19+ individuals.

Primary outcome variable(s)

The primary outcome is the change in amount of SARS-CoV-2 in the oral cavity before and after intervention.

Secondary outcome variable(s)

Subjects clinical status at day 7 and the number of COVID-19 symptoms, symptoms onset and the severity of symptoms will be collected throughout Phase 2 of the study.

Background

Severe acute respiratory syndrome, or SARS is caused by a novel coronavirus termed the SARS coronavirus, or SARS-CoV-2, spreads through droplet infection produced when the infected person speaks, coughs, or sneezes, and affects people of any age. The epidemic of coronavirus disease 2019 (COVID-19) caused by SARS-CoV-2, originating in Wuhan, China, has become a major public health challenge for not only China but also countries around the world. [1] The disease has affected vulnerable individuals, especially those with co-morbidities. [1]

The incubation period for SARS-CoV2 is widely considered to be 2-7 days, but occasionally may last up to 10 days. Most patients identified up to now were previously healthy adults aged 25 through 70 years. [3] Dentists have been alarmed by the spread of SARS-CoV-2 in clinical facilities, where a disproportionately large number of health care workers (HCWs) have been infected in major hospitals treating infected individuals worldwide. Due to the characteristics of dental settings, the risk of cross infection can be high between patients and dental practitioners as the infection typically enters through mouth, nose, and eyes making dentistry one of the medical practices at highest risk of infection due to the frequent production of aerosols and the constant presence of saliva.

According to the World Health Organization (WHO), close contact with or short-range transmission of infectious saliva droplets is a primary mode for SARS-CoV-2, while long-distance saliva aerosol transmission is highly environment-dependent.

Dental practices, which operate indoors with a high volume of aerosol-generating procedures, are a high-risk environment if the appropriate precautions are not taken. [4] Saliva stands at the entry of the respiratory system and has been found to be SARS-CoV-2 nucleic acid positive. [5-7] Besides the lungs, salivary glands and tongue are possibly other hosts of SARS-CoV-2 due to expression of angiotensin-converting enzyme II (ACE2). Several studies have shown that ACE2 play a crucial role in the entry of the virus into the cell to cause the final infection, making the oral cavity a potential reservoir for SARS-CoV-2. [8-11] Preliminarily, these findings may explain the basic mechanism that the oral cavity is a potentially high risk for SARS-CoV-2 infectious susceptibility and provide evidence for the future prevention strategy for dental practices in areas that are potentially affected with COVID-19 and where additional effective infection control protocols are urgently needed. Current guidelines from the US Center for Disease Control (CDC), WHO, and the American Dental Association (ADA) have stressed the importance of personal hygiene measures and social distance approaches for SARS-CoV-2 prevention.

In addition, personal protective equipment (PPE) guidelines have been established to protect the skin and mucous membranes of the eyes, nose, and mouth from exposure to potentially infectious material. These infection control measures are critical for preventing the spread of community acquired disease, nevertheless additional measures are needed in dental care settings to prevent the spread of disease between providers and patients when treating patients with known infective or high-risk individuals.

These measures should be focused on reducing the viral load in the nasopharynx and oropharynx in patients who are high-risk or COVID-19 positive prior to delivering aerosol generating dental interventions. Past research studies on infections similar to COVID-19 have shown the efficacy of targeted mouthwash solutions such as chlorhexidine gluconate (CHG), polyvinylpyrrolidone iodine (PVP-I), saline solutions (SS), and hydrogen peroxide (H₂O₂) amongst others on reducing viral load against respiratory and oral track pathogens. [12-18] Efficacy in the reduction of viable bacteria in dental aerosols by procedural rinsing with an antiseptic mouth rinse has been demonstrated to potentially reduce the risk of cross-contamination in the dental operator. [19]. The ADA (2020) has issued interim guidelines for minimizing the risk of COVID-19 transmission from the patient to the dental professional recommending the use of a preoperative 0.2% PVP-1 mouth rinse. The use of PVP-1 mouth rinse has also been recognized by the Centers for Disease Control and Prevention. Challacombe et al. suggests that all patients requiring dental treatment should be administered a 9 mL of the 0.5% solution as a mouth rinse (30 s for gentle gargling). [19] However, until now, only a few *in vivo*, *in vitro* and *in silico* studies have been conducted to support the recommendation of mouth rinses to control the viral load and manage the risk of COVID-19 infections in the dental office and the community. Clinical trials evaluating the potential applications of existing mouth rinses is essential to gaining an understanding of the anti-SARS-COVID-19 activities of active ingredients like PVP-1. In summary, PVP-1 has the potential to be a simple, affordable and effective preventive therapy to rapidly inactivate SARS-CoV-2 and may play an adjunctive role in mitigating viral transmission beyond personal protective equipment.

Study Design

Phase*

Phase II

Design

Phase I: Study participants will complete a one-time study visit and will be asked to rinse/gargle with 10ml of the assigned mouthwash for 30 seconds. Subjects will be randomized to either rinse/gargle with Povidone-iodine 0.5% or a placebo. Phase II: Study participants will be given a 1 week supply of Povidone-iodine 0.5% mouth rinse and will be asked to rinse/gargle with 10ml for 30 seconds 4 times per day. Subjects will be contacted on Day 7 using Telemedicine, phone calls, and/or text messages to determine clinical status.

Study duration

Phase I: 1 day Phase II: 1 week

Characteristics of the Study Population

Target population

Forty (40) subjects with confirmed clinical diagnosis of COVID-19 and at least one onset clinical sign will be recruited and randomized in the study. If there are screen failures, more than 40 subjects may consent. Subjects who sign the informed consent form and are randomized and receive the study product, and subsequently withdraw, or are withdrawn or discontinued from the study, could be replaced at the investigators discretion. For example, if a subject's samples are found to be less than optimal.

Subjects enrolled by Penn Researchers

40

Key inclusion criteria

1. Able and willing to provide informed consent prior to initiation of study procedures. 2. Stated willingness to comply with all study procedures and availability for the duration of the study. 3. Male or female, aged 18 years and older. 4. Clinical diagnosis of COVID-19 infection confirmed with a positive point of care test. 5. Confirmed diagnosis within 5 days of baseline visit (within 5 days of COVID-19 test) and at least one clinical COVID-19 symptom [*Signs and symptoms of COVID-19 present at onset, but over the course of the disease, most people will experience the following: fever or chills, cough, shortness of breath or difficulty breathing, fatigue, muscle or body aches, headache, new loss of taste or smell, sore throat, congestion or runny nose, nausea or vomiting and diarrhea.] 6. Presents with a minimum of six natural teeth. 7. Ability to rinse/gargle with study products. 8. Not using mouth rinse/gargling solutions at the time of enrollment. 9. Not taking antimicrobial medications (antibacterial, antiviral, antibiotics, including hydroxychloroquine) at time of enrollment. 10. Ability to participate in the study and come to site during Phase I of the study for collection of swabs and saliva. 11. Willing to use an acceptable method of birth control throughout duration of the study. Acceptable methods include hormonal contraceptives, barrier methods, abstinence, or other effective methods approved by the PI. 12. If continuing to Phase II of the trial, ability to continue using study products for 1 week (+ 3 days). (Participants do not have to agree to participate in Phase II in order to participate in Phase I.) 13. If continuing to Phase II of the trial, agree to receive text messages/phone calls containing questionnaires regarding compliance and use of study product, and reminders, able to complete virtual follow-up study visit for collection of outcomes data.

Key exclusion criteria

1. Individuals receiving antiviral medications 2. Pregnant or breastfeeding women (for premenopausal women of childbearing potential, pregnancy status to be confirmed through a urine pregnancy test during the study visit) 3. Inability to comply with study protocol 4. Having an allergy to any of the study mouthwash ingredients 5. Having any thyroid condition. 6. Presents with a current suspicious oral lesion at the examiners discretion, and/or currently undergoing radiation therapy for head or neck cancer, and/or has received radiation therapy to the head or neck (including radioactive iodine therapy).

Populations vulnerable to undue influence or coercion

Although not directly targeted, mentally disabled persons, economically or educationally disadvantaged person, and/or employees or students of the University of Pennsylvania will not be denied enrollment and any special protections an/or additional safeguards will be undertaken in order to protect the rights and welfare of these subjects from coercion or undue influence as appropriate.

Subject recruitment

COVID-19+ patients will be recruited to achieve 40 study subjects who enroll in and are eligible for study participation. Primary recruitment will be through the University of Pennsylvania testing sites. We will also place flyers within our hospitals and dental clinics, including our community health centers outside the school. Subjects who present a positive COVID test and at least one COVID symptom (see inclusion criteria) will be recruited. Email messages advertising using an IRB approved template the study will also be sent out to University of Pennsylvania mailing lists that include faculty, staff, and students.

Will the recruitment plan propose to use any Penn media services (communications, marketing, etc.) for outreach via social media avenues (examples include: Facebook, Twitter, blogging, texting, etc.) or does the study team plan to directly use social media to recruit for the research?

Yes

Subject compensation*

Will subjects be financially compensated for their participation?

Yes

If there is subject compensation, provide the schedule for compensation per study visit or session and total amount for entire participation, either as text or separate document

Baseline/Visit 1 can be done in one visit with confirmatory diagnosis of COVID and after inclusion/exclusion is met. If a subject is a screen failure during Phase I for any reason and is unable to be enrolled, they will receive \$20. Phase I: \$100 Phase II: \$20 for attending the remote visit on Day 7 Subjects will be compensated through Greenphire ClinCard. If a subject does not have a social security number, he/she will be compensated via an Amazon gift card.

Study Procedures

Procedures

At the Screening/Baseline visit, the following procedures will be performed: Informed consent will be obtained; Demographic information will be obtained; Vital signs measurements will be performed (temperature, blood pressure, heart rate, height, weight); Oral health questionnaire; A clinical oral exam will be completed; Dental and Medical history will be reviewed to determine eligibility based on inclusion/exclusion criteria; A point of care COVID-19 test will be completed to determine eligibility based on inclusion/exclusion criteria; Premenopausal women of child bearing potential will complete a urine pregnancy test to confirm eligibility; Eligible subjects will be randomized to one of two treatments; Randomized subjects will rinse with 10 ml of their assigned product for 30 seconds; Swab samples (posterior dorsal tongue and nasal swabs) will be collected at Baseline (pre-rinse) and at 5, 30 and 60 minutes post-rinse; Salivary samples will be taken at Baseline (pre-rinse) and at 5, 30 and 60 minutes post-rinse; Subject who successfully complete Phase I will be invited to continue into Phase II of the clinical trial and given the product to take home to use as instructed. If continuing they may be scheduled for a remote follow-up visit on Day 7. If not continuing the subject will be exited from the clinical trial after Visit 1. Phase II Visit 2 (Day 7 +/- 3 Days): Medical history will be updated. This visit will be completed remotely via the collection of questionnaires. Subjects will be sent a link to the questionnaires via text message or email, and/or be contacted via phone or telemedicine. Questionnaires will collect outcomes data assessing their clinical status, number of COVID-19 symptoms, symptoms onset and the severity of symptoms. At this timepoint subjects will exit the study. A separate modification request will be submitted at the time a pregnancy is identified, before any follow-up on incidental pregnancy will occur. At that time, the pregnancy supplemental form, along with a description of the data and method of collection (i.e. via self-report, medical chart review, questionnaires, etc.) will be provided.

STATISTICAL CONSIDERATIONS

Statistical Hypotheses (Phase 1 ONLY)

For the study, the null hypothesis (H_0): $\delta = 0$ and the alternative hypothesis (H_1): $\delta \neq 0$. The type of comparison in all cases will be superiority. Our primary endpoint is the percentage reduction of SARS-Co-V-2 load at 60 minutes (post-intervention) compared to baseline between the PVP-I mouthwash versus the placebo mouthwash. The secondary endpoints are the respective percentage reductions of SARS-Co-V-2 load at both 5 and 30 minutes (post-intervention) compared to baseline between the PVP-I mouthwash versus the placebo mouthwash.

Sample Size Determination

Assumptions:

- Looking to determine the value of the difference in the percentage reduction of SARS-Co-V-2 load at 60 minutes (post-intervention) compared to baseline between the PVP-I mouthwash versus the placebo mouthwash.
- Will use a two sample t-test assuming equal variance and sample size in each of the two arms
- δ is the difference between population means at which power and sample size calculations are made.
- Null hypothesis (H_0): $\delta = 0$, Alternative hypothesis (H_1): $\delta \neq 0$
- Trying to determine necessary sample size to show a significant difference under the alternative hypothesis by assuming a 20% greater difference (PVP-I versus placebo) in the reduction of SARS-Co-V-2 load after 60 minutes and a corresponding standard deviation for both groups of 0.20.
- Alpha (probability of Type-I error [true null hypothesis is rejected]) of 0.05
- Power (probability of rejecting a false null hypothesis) of 0.80
- We will assume 20% dropout rate in calculating the final # of patients to be enrolled

For the desired 80% power, the necessary sample size(s) is calculated to be n=34 (17 per arm). After accounting for the aforementioned 20% dropout, 44 patients will be enrolled in the study (22 per arm). The power calculations were performed using PASS Software 20.0.3.

General Approach

Descriptive statistics will be used to compare characteristics of the two groups (PVP-I mouthwash and placebo mouthwash. Group randomization will occur prior to the study visit using block randomization with block sizes randomly chosen as 4 or 6. Categorical variables will be described by frequencies, whereas continuous variables will be described using ranges, means, medians, and inter-quartile ranges and compared between groups using either the Chi-square test for binomial proportions or the Fishers' exact test as needed. Continuous variables will be compared using either a t-test for independent groups or the Mann-Whitney for cases where normality is not a reasonable assumption. All statistical tests will be two tailed, with an alpha level of 0.05.

Note that we may not be able to adjust for anything (or the adjustments will have to be very limited in scope and breadth) due to sample size issues.

Analysis of the Primary Efficacy Endpoint(s)

As described earlier, the primary endpoint is the percentage reduction of SARS-Co-V-2 load at 60 minutes (post-intervention) compared to baseline between the PVP-I mouthwash versus the placebo mouthwash. Assuming normality is a reasonable assumption, this percentage reduction will be compared between the two mouthwash groups (PVP_I versus placebo) using a t-test. Results will be presented as means and standard deviations with corresponding 95% confidence intervals and p-values.

Note that missing data should not be a concern as the cross-sectional study is a single visit.

Analysis of the Secondary Endpoint(s)

The secondary endpoints are the percentage reduction of SARS-Co-V-2 load at both 5 and 30 minutes (post-intervention) compared to baseline between the PVP-I mouthwash versus the placebo mouthwash. Assuming normality is a reasonable assumption, these respective percentage reductions will be compared between the two mouthwash groups (PVP_I versus placebo) using a t-test. Results will be presented as means and standard deviations with corresponding 95% confidence intervals and p-values.

Note that missing data should not be a concern as the cross-sectional study is a single visit.

Safety Analyses

Safety data will be collected at all study visit through solicitation of adverse events from subjects. Safety data will also be collected throughout the duration of the study via the subject's medical records.

All subject reported and evaluator observed adverse events will be collected documented on the appropriate CRF. Only related adverse events will be reported for this research study. Expected related adverse events include gingival/mucosal irritation and allergic reaction to study products.

Baseline Descriptive Statistics

Baseline (including demographic) characteristics will be summarized by standard descriptive statistics (including mean and standard deviation for continuous variables such as age and standard percentages for categorical variables such as gender). This will be done for both the overall cohort and stratified by mouthwash solution (antiseptic versus placebo). The baseline characteristics will be compared across the two mouthwash groups using Fisher's Exact test for categorical variables and t-tests for continuous variables (also accounting for equal versus unequal variance across the groups).

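### Randomized, treated subjects may be replaced at discretion, with no sample-adequacy criterion, no allocation rule for replacements and no statement on keeping their data; the missing-data notes and the 40-versus-44 target do not fit the plan's own 20% dropout

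*Combined protocol and SAP*

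**What the plan says.** **Replacement.** The Target population section deals with subjects who have consented, been randomized and received product. Those who "subsequently withdraw, or are withdrawn or discontinued from the study, could be replaced at the investigators discretion". The one example is that a subject's "samples are found to be less than optimal".

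**Endpoint.** The Primary outcome variable(s) section states: "The primary outcome is the change in amount of SARS-CoV-2 in the oral cavity before and after intervention". The Statistical Hypotheses section, which covers Phase I only, makes this the percentage reduction in "load at 60 minutes (post-intervention) compared to baseline between the PVP-I mouthwash versus the placebo mouthwash". Under Procedures, tongue and nasal swabs and saliva are taken before the rinse and at 5, 30 and 60 minutes after it.

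**Missing data.** The analysis sections for the primary and the secondary endpoints each carry a note that missing data need not be a worry, because the study is one visit. The sample-size assumptions state: "We will assume 20% dropout rate in calculating the final # of patients to be enrolled".

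**Numbers.** Target population: "Forty (40) subjects with confirmed clinical diagnosis of COVID-19" are to be recruited and randomized. Subject recruitment: "patients will be recruited to achieve 40 study subjects who enroll in and are eligible for study participation". Sample Size Determination: 34 evaluable (17 per arm), raised to 44 enrolled (22 per arm).

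**Blinding.** Abstract: "Phase I will be double blinded clinical trial of the safety and efficacy".

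No analysis population is named anywhere in Statistical Considerations.

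**The concern.** Replacement here happens after randomization and after the rinse, and its only example concerns the material from which the primary endpoint is measured. The plan leaves four things open:

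- what makes a sample inadequate, and who decides;
- whether the decision is made without sight of the viral-load result;
- which arm a replacement enters;
- whether the replaced subject's measurements stay in the analysis.

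Two situations need to be kept apart. If usable data are set aside for reasons linked to the outcome, the comparison loses the protection of randomization, and that loss is avoidable. If a 60-minute sample is truly unusable, there is no value to keep. Replacement does not cause that bias, and only reporting and a sensitivity analysis can reveal it. The plan has no rule to prevent the first or reveal the second.

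The missing-data notes make this worse. One visit does not guarantee a usable oral specimen at both baseline and 60 minutes, and the plan itself foresees poor samples and 20% loss.

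**Working it through.** **1. The plan's own sample size.** Inputs from Sample Size Determination and General Approach: difference 0.20, SD 0.20 per arm, two-sided alpha 0.05, power 0.80, equal-variance two-sample t-test, 20% dropout.

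- Standardized effect = 0.20 / 0.20 = 1.
- Noncentral t solution: n = 16.71, so 17 per arm and 34 in total; power at 17 per arm is 80.7%.
- Dropout: 17 / (1 - 0.20) = 21.25, so 22 per arm and 44 in total.

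Both stated figures reproduce.

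**2. Forty against forty-four, with loss unrelated to outcome.**

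| Randomized | Per arm | After 20% loss | Power |
|---|---|---|---|
| 40 | 20 | 20 x 0.8 = 16 | 78.1% |
| 44 | 22 | 22 x 0.8 = 17.6, at least 17 | 80.7% at 17 |

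Forty keeps 17 per arm if no more than three per arm are lost (20 - 3 = 17); 44 does so with up to five (22 - 5 = 17). With no loss, power is 86.9% at 20 per arm and 90.0% at 22.

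**3. How much replacement could matter.** The documents give no rate or pattern of inadequate samples, so these are assumed patterns and not estimates. Setting: 20 per arm, normal outcomes, SD 20 points, planned t-test, simulated. Each replacement enters the arm of the subject lost, which is itself an assumption.

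*Moderate, arm-blind.* Subjects are chosen from all 40 on an adequacy score correlated 0.3 with the size of the reduction, then dropped and replaced. With a true effect of 20 points and one to four replacements, the mean estimate is about 19.6-19.9 points and power about 86%, against 86.9% with no loss.

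*Extreme, arm-blind.* The one to four largest reductions are always the ones dropped and replaced. Because PVP-I works in this scenario, 86-91% of those lost are PVP-I subjects. The estimate falls to 18.5, 17.5, 16.8 and 16.3 points, and power to 84.5%, 82.6%, 80.9% and 79.9%. With no true effect, the same arm-blind selection leaves type I error at 4.9-5.2%.

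*Extreme, one arm only, no true effect.* The least-reduced subjects in one arm are lost:

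| Lost | Dropped and replaced | Missing, not replaced | Data kept, replacements added |
|---|---|---|---|
| 1 | 6.8% | 6.8% | 5.0% |
| 2 | 9.4% | 10.0% | 5.0% |
| 3 | 12.6% | 14.4% | 5.0% |

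At correlation 0.3 in place of perfect ordering, the first two columns become 5.1-5.7%. If the same number of least-reduced subjects is dropped and replaced in each arm (one to four), there is almost no bias in the estimate and type I error is 6.5-8.2%.

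*Sensitivity to the allocation assumption.* Allocating replacements 50:50 moves the three-subject one-arm figure from 12.6% to 13.5%, and the four-subject arm-blind power from 79.9% to 77.5%.

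**The case against.** **The rule may be about recruitment only.** It sits beside the sentence on screen failures and says that subjects could be replaced, not that their data are removed. This stands in part. A reader might infer that the plan discards usable data; no section says so. What the text supports is silence on whether the data are kept.

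**Phase I is double blind.** This makes deliberate arm-specific replacement unlikely, and a reader should not infer from the 7-13% figures that the trial's type I error is inflated. Those figures need three conditions together: losses in one arm only, adequacy ordered perfectly by outcome, and data dropped. The documents establish none of them. But blinding to arm is not blinding to the assay result, and the latter is nowhere required. The documents neither show nor exclude that sample adequacy after the rinse differs by arm.

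**One visit of about an hour should lose few subjects.** This is fair for attrition between samples. It does not cover unusable specimens. Nor can the 20% dropout be put down to Phase II, since the hypotheses and sample size concern Phase I.

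**Forty may still be enough.** It is, if losses stay at three per arm or fewer. Replacement might also be meant to stand in for over-enrolment to 44, but the plan does not say so. The allowance for more than 40 consents concerns screen failures, not randomized subjects.

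**Conclusion.** The gap in the text is certain and should be fixed before analysis; the harm from it is conditional. Under double blinding with weak outcome-related selection, replacing a few subjects costs almost nothing: about 19.6-19.9 of 20 points and about 86% power, assuming correlation 0.3, one to four replacements and same-arm allocation. The type I error of about 7-13% marks only the extreme end for one to three subjects in one arm. The documents do not support reading it as expected bias.

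Two contradictions need no assumed selection pattern. The missing-data notes conflict with the 20% dropout and with the provision for poor samples. The target of 40 conflicts with 44, and at the plan's own loss rate 40 gives 78.1% power against the stated 80%. That shortfall is small and is a separate matter from replacement.

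**What to change.** 1. **Analysis set.** Analyse all randomized subjects who received product, in the assigned arm, and keep every available measurement of anyone withdrawn or replaced. Replacements are added, not substituted, and take the next unused assignment on the blocked randomization list. State that the primary t-test uses those with usable baseline and 60-minute values, so it is a complete-case analysis.
2. **Sample adequacy.** Allow a sample to be called inadequate only on a prespecified objective criterion, judged blind to arm and without reference to the viral-load result.
3. **Missing data.** Delete both notes. Report unusable samples by arm and time point. Add one sensitivity analysis: multiply impute missing 60-minute reductions within arm, then shift the imputed PVP-I values down by 0, 10 and 20 points, leaving imputed placebo values unshifted. For scale, with 4 of 20 PVP-I values missing, the 20-point shift lowers that arm's mean by 4/20 x 20 = 4 points.
4. **Separately, the target number.** Reconcile 40 with 44, or keep 40 and restate power as about 78% at 20% loss.

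The cost is protocol and SAP wording, one extra analysis, and either four more subjects (already in the sample-size section) or a slightly lower stated power. The planned t-test is unchanged.

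### The primary percentage reduction has no value when the pre-rinse oral load is undetectable, and the plan has no rule for such subjects

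*Combined protocol and SAP*

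**What the plan says.** **Entry.** Key inclusion criteria, item 4, asks for "Clinical diagnosis of COVID-19 infection confirmed with a positive point of care test". Item 5 adds a diagnosis within 5 days of the baseline visit and at least one symptom. Under Procedures, the screening/baseline visit includes a further check: "A point of care COVID-19 test will be completed to determine eligibility based on inclusion/exclusion criteria". Neither section gives that test's specimen type or a threshold for load.

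**Order of events.** Procedures lists eligibility, randomization, the rinse and all sampling (pre-rinse, then 5, 30 and 60 minutes) for the same visit. General Approach places randomization before the visit. Neither section makes a baseline load result a condition for going on.

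**Endpoint.** Statistical Hypotheses (Phase 1 ONLY) states: "Our primary endpoint is the percentage reduction of SARS-Co-V-2 load at 60 minutes (post-intervention) compared to baseline". The arms are compared by t-test.

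**Incomplete data.** Analysis of the Primary Efficacy Endpoint(s) says: "Note that missing data should not be a concern as the cross-sectional study is a single visit". Target population lets the investigator replace subjects who leave or are withdrawn after being randomized and receiving product, and gives this illustration: "For example, if a subject's samples are found to be less than optimal".

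**Sample size.** Sample Size Determination arrives at 17 per arm for 80% power, raised to 22 per arm (44) for 20% dropout. Target population and Subject recruitment give 40.

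**The concern.** The pre-rinse load is the denominator of the primary endpoint. If it is zero or below the assay's limit, the percentage reduction is 0/0 or an unbounded negative number. This can happen with perfect attendance, so having a single visit does not prevent it.

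The documents state no assay, detection limit, evaluable population or rule for this case. An analyst would have to choose between dropping these subjects, scoring them as zero reduction, or entering a limit value. The choices give different estimates, and the plan leaves the choice open until results are in hand.

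The replacement clause adds a second opening. Nothing ties the judgement that a sample is poor to pre-rinse material, or requires whoever makes it to be unaware of arm and post-rinse results. Replacement that can depend on post-rinse findings can bias a randomized comparison. Power is also at stake, because the 17 per arm must be subjects with a computable endpoint.

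**Working it through.** **Inputs from Sample Size Determination and General Approach:** difference δ = 0.20, SD = 0.20 in both arms, two-sided α = 0.05, equal-variance two-sample t-test, 1:1 allocation, dropout d = 20%. **Assumed, because the documents give no figure:** the undetectable share u, shown at 10%, 20% and 30%.

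**Step 1: reproduce the plan.** Power comes from the noncentral t distribution with 2n − 2 degrees of freedom and noncentrality δ / (SD × √(2/n)). At n = 16 per arm it is 78.1%; at n = 17 it is 80.7%. So 17 per arm (34) is right. Enrolment is 17 / 0.8 = 21.25, rounded up to 22 per arm (44). Both stated figures reproduce.

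**Step 2: exclude subjects with an undetectable baseline.** Evaluable n per arm = (N/2) × (1 − d) × (1 − u), rounded down.

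| u (assumed) | 44, no dropout | 44, 20% dropout | 40, no dropout | 40, 20% dropout |
|---|---|---|---|---|
| 0% | 22: 90.0% | 17: 80.7% | 20: 86.9% | 16: 78.1% |
| 10% | 19: 85.1% | 15: 75.3% | 18: 83.0% | 14: 72.1% |
| 20% | 17: 80.7% | 14: 72.1% | 16: 78.1% | 12: 64.9% |
| 30% | 15: 75.3% | 12: 64.9% | 14: 72.1% | 11: 60.7% |

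Each cell gives evaluable subjects per arm, then power. Rounding down lowers some cells: 22 × 0.8 × 0.9 = 15.84 is entered as 15 (75.3%), whereas 16 would give 78.1%.

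**Step 3: the share the plan can absorb.** With no dropout, 34 evaluable subjects remain up to u = 1 − 34/44 = 22.7% at 44 enrolled, or 1 − 34/40 = 15% at 40.

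**Step 4: keep them as zero reduction.** At u = 20% the expected difference falls from 0.20 to 0.8 × 0.20 = 0.16. The spread within an arm also changes, because zeros are mixed with values around that arm's mean. The effect therefore depends on the placebo mean, which the plan does not give. Simulated power of the planned t-test:

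| Subjects per arm | Placebo mean 0 | Placebo mean 0.20 |
|---|---|---|
| 22 (no dropout) | about 80% | about 65% |
| 17 (dropout fully used) | about 68% | about 53% |

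**Step 5: enrolment if both losses occur in full.** Per arm, 17 / (0.8 × (1 − u)), rounded up: 24, 27 and 31 for u = 10%, 20% and 30%, or 48, 54 and 62 in total.

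**The case against.** A reader might infer that the trial will miss its 80% power. The documents do not support that. The undetectable share is unknown, and Phase I is one visit with its last sample at 60 minutes, so dropout may be close to nil. The 20% allowance would then be free to cover non-evaluable subjects, up to about 23% of 44. This stands, and it is why the loss is called possible and not shown. It has limits. The plan assigns that allowance to dropout alone, it shrinks to 15% if 40 is the real target, and with 40 enrolled the plan's own 20% dropout already leaves 16 per arm (78.1%) before any baseline is lost.

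A reader might also infer that undetectable baselines are likely because the diagnosis may be 5 days old. The point-of-care test at the screening/baseline visit weakens that reading: item 4 together with Procedures implies a positive result on the day. It does not guarantee measurable virus in saliva or on the tongue, since the test's specimen and sensitivity are not stated.

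A change of scale is a partial answer. A log10 change with a fixed value below the limit is defined for everyone. But a subject already at the limit before the rinse still cannot show a fall, so dilution remains and a rule is still needed.

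Finally, the replacement clause could be used sensibly, for pre-rinse failures only. Nothing shows it would be misused; the point is that the text does not restrict it.

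**Conclusion.** The missing rule is established from the documents alone: the endpoint needs a measurable baseline, entry does not secure one, and neither the missing-data statement nor the replacement clause says what happens without one. This holds whatever the share turns out to be.

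The effect on power is conditional. With exclusion, power stays at 80% or above if dropout is negligible and the share is below about 23% (44 enrolled) or 15% (40 enrolled). It falls below 80% if the losses come on top of the planned dropout. Keeping such subjects as zero can cost more, depending on the placebo mean. All of this rests on the plan's δ and SD and on assumed values of u.

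This is a cheap improvement to the plan. It is not evidence that the sample size is wrong.

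**What to change.** **Analysis of the Primary Efficacy Endpoint(s).** Name the one oral specimen that carries the primary endpoint (tongue swabs and saliva are both collected) and state the assay and its detection limit. Define the primary analysis set as all randomized subjects whose pre-rinse load in that specimen is quantifiable, decided from pre-rinse data only by staff blinded to arm. Membership then depends on a measurement taken before the rinse, so treatment cannot affect it. Give post-rinse results below the limit one fixed value. Report exclusions by arm, and add a sensitivity analysis that keeps all randomized subjects. Delete the statement that missing data are no concern, here and where it is repeated for the secondary endpoints.

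**Target population.** Do not allow replacement on the basis of post-rinse sample results.

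**Sample Size Determination.** Reconcile the enrolment target (40 or 44), state that the 20% allowance covers dropout and non-evaluable baselines together, and restate power for the expected evaluable number.

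**Cost.** Wording only, with no new samples. The primary result will apply to people with measurable oral virus, and the stated power may be less favourable. If the sponsor expects both losses in full and wants to hold 80%, enrolment would have to rise as in Step 5.
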